2.9 Angiogenesis, VEGF, and Cervical Cancer

In patients with cervical neoplasia, VEGF expression and microvessel density progressively increased during the transition of normal cervical epithelium to squamous cell carcinoma [92]. Furthermore, polymorphisms of VEGF genes may correlate with survival of early stage cervical cancer by modulating angiogenesis as measured according to microvessel density [93]. In the animal laboratory model, increased tumor vascularization and enhanced expression of VEGF and matrix metalloproteinase-2 and -9 in tumor cells in stressed animals could be abrogated by the use of a β -adrenergic antagonist such as propranolol [23]. Extrapolating from this data and recognizing that the HPV-18 E6 oncoprotein induces VEGF transcription in a p53-dependent manner, decreasing the expression of VEGF in tumor cells by reducing the stress response may be an interesting method of cervical cancer therapy [94]. This is substantiated by the fact that VEGF receptor 2 is more highly expressed in cervical cancer cells than in normal cervical tissue controls [92, 93, 95]. High vascularity as measured according to microvessel density is associated with a positive lymph node status [96], poor prognosis, and increased risk of recurrence [97]. Five-year survival rates for cervical tumors with high and low microvessel densities are 50% and

65%, respectively [98]. Finally, serum VEGF levels are significantly elevated in cervical cancer patients with large and/or high-grade tumors or who smoke [95].

2.10 Cervical Cancer Cell Lines, Cervical Cancer Tissue, and Adrenergic Receptors

In our lab we evaluated human cervical cancer samples obtained at the time of diagnosis from 168 women. ADRB1 and ADRB2 expression was examined using immunohistochemical peroxidase staining and semi-quantitative scores were related to patient outcome. In addition, we examined the effects of catecholamines on production of pro-angiogenic factors (VEGF, IL8) by cervical cancer cell lines (SiHa and Caski) using qRT-PCR.

The median age of patients was 45.3 (range 22 – 83). Among the 168 tumor samples evaluated, 85% had increased ADRB1 expression and 61% had increased ADRB2 expression. Tumor stage or grade were not related to ADRB expression. ADRB1 expression was not related to overall patient survival ($p = 0.86$); however, ADRB2 was significantly related (mean 146 months for those with increased expression vs. 206 months for those with low or absent expression; $p = 0.038$). Upon stimulation with norepinephrine or isoproterenol, the levels of VEGF did not change appreciably, but the levels of IL8 increased by 3.5 – 6-fold ($p < 0.001$). These data support the hypothesis that ADRB2 might play a pivotal role in cervical cancer growth and progression and have potential clinical implications for new therapeutic strategies.

2.11 Summary

Women diagnosed with recurrent cervical cancer are faced with a dearth of effective chemotherapy or other therapies in a recurrent setting; thereby, using a low side effect drug such as propranolol beneficial in a population with such a short time of overall survival is appropriate. There are many other downstream effectors of the beta-adrenergic receptor which are equally important in carcinogenesis that will need to be explored in the future.

Because β -blocker use has been prevalent in patients with cardiovascular disease for years, they are known to be safe and offer the relatively inexpensive opportunity to test our hypothesis regarding the effects of neurobiological stressors on cervical cancer in our proposed study. Our hypothesis is that the intervention of a beta-adrenergic blockade in conjunction with “minimal dose” relaxation intervention in advanced cervical cancer patients will result in stable to improved quality of life and improved overall survival. This improved QOL and OS will correlate with decreases in serum levels of interleukin 6 and 8 and VEGF. Furthermore, attention to QOL at the end of life has become of the utmost importance in caring for patients with advanced cancer. ASCO recently supported the emphasis on best supportive care in stating that “substantial evidence demonstrates that palliative care—when combined with standard cancer care or as

the main focus of care—leads to better patient and caregiver outcomes.” These include improvement in symptoms, QOL, and patient satisfaction, with reduced caregiver burden. Earlier involvement of palliative care also leads to more appropriate referral to and use of hospice, and reduced use of futile intensive care [19] The proposed study emphasizes avoidance of treatment of recurrent incurable cervical cancer with standard second line therapies, in which response durations have been dismal. Instead, this proposal integrates an R/GI therapy intervention and low-risk treatment with a β -blocker, which is supported by strong preclinical and retrospective data and expected to result in maintained OS decreased distress and improved quality of life.

3.0 PATIENT ELIGIBILITY

3.1 Inclusion:

- 3.1.1 Proven recurrent cervical cancer of any histology not eligible for curative radiotherapy or surgery.
- 3.1.2 Failed chemotherapy for first recurrence (excluding chemotherapy with concurrent irradiation) or refractory to first line systemic therapy.
- 3.1.3 Measurable or non-measurable disease
- 3.1.4 Unlimited prior therapies

3.2 Exclusion:

- 3.2.1 Patients whose disease may be cured by surgery or radiotherapy.
- 3.2.2 Contraindication to use of a β -blocker.(uncontrolled DM, COPD-unstable, Bradycardia <50 BPM)
- 3.2.3 Already receiving a β -blocker.
- 3.2.4 Performance status > 3. Must have had treatment for first line recurrence
- 3.2.5 Prior radiation therapy for localized cancer of the breast, head and neck, or skin is permitted provided that it was completed more than 3 years prior to registration, and the patient remains free of recurrent or metastatic disease.
- 3.2.6 With the exception of non-melanoma skin cancer and other specific malignancies as noted above, patients with other invasive malignancies who had (or have) any evidence of the other cancer present within the last five years or whose previous cancer treatment contraindicates this protocol therapy are excluded.

- 3.2.7 Use of systemic glucocorticoids such as Prednisone or Decadron in the last month for greater than one week
- 3.2.8 Inability to accurately answer questions (e.g. dementia, brain metastases) or speak English or Spanish.
- 3.2.9 Cirrhosis of the liver
- 3.2.10 Patients under the age of 18
- 3.2.11 History of comorbid conditions: Addison's disease, autoimmune hepatitis, hepatitis B, hepatitis C, AIDS or HIV, lupus erythematosus, mixed connective tissue disease, rheumatoid arthritis.
- 3.2.12 Hypersensitivity to propranolol, or beta-blockers
- 3.2.13 Uncompensated congestive heart failure
- 3.2.14 Cardiogenic shock
- 3.2.15 Severe sinus bradycardia; heart block, second or third degree or sick sinus syndrome (if no artificial pacemaker present)
- 3.2.16 Severe hyperactive airway disease (chronic obstructive pulmonary disease, asthma)
- 3.2.17 Any patients on Avastin or any other anti-angiogenic drugs.
- 3.2.18 Patients with brittle diabetes mellitus (DM) Brittle diabetes mellitus is a type of diabetes when a person's blood glucose (sugar) level often swings quickly from high to low and from low to high. Also called "unstable diabetes" or "labile diabetes."
- 3.2.19 Patients participating in or who plan to participate in other trials during the course of this study.
- 3.2.20 Patients actively using cocaine.
- 3.2.21 Cannot be receiving any other active neoplastic treatment during 4 months of study.

4.0 STUDY MODALITIES

4.1 Propranolol (Inderal[®])

4.1.1 Indication and Use:

Used for treatment of hypertension, cardio protection after a myocardial infarction, and management of cardiac arrhythmias such as atrial fibrillation. Also it can be used in the treatment of migraines or essential tremor.

4.1.2 Formulation:

Propranolol is supplied as tablets in the following strengths: 10 mg, 20 mg, 40 mg, 60 mg, and 80 mg.

4.1.3 Storage:

Store tablets at room temperature between 20-25°C (68-77°F) and away from light and moisture

4.1.4 Administration:

A starting dose of propranolol 20 mg is taken by mouth twice a day (40 mg/day). If the patient tolerates the initial dose (no hypotension or bradycardia) the dose will be increased to 40 mg by mouth twice a day at the start of the second month of therapy. For patients >65 years old the dose will stay at 20 mg by mouth twice a day. Dose reductions to 10 mg administered by mouth twice a day will be allowed for titration for optimization of BP and pulse. All dose adjustments will be made in the clinic.

4.1.5 Onset and Duration of Action:

Propranolol is administered orally or intravenously. After oral administration of immediate-release propranolol, the dose is almost completely absorbed, and peak concentrations are achieved within 60-90 minutes. Co-administration with food appears to enhance bioavailability.

Despite complete absorption, propranolol has a variable bioavailability due to extensive first-pass metabolism. Hepatic impairment will therefore increase its bioavailability. The main metabolite 4-hydroxypropranolol, with a longer half-life (5.2-7.5 hours) than the parent compound (3-4 hours) is also pharmacologically active.

4.1.6 Metabolism and Excretion:

Propranolol is highly lipophilic and, as a result, is widely distributed throughout the body. It readily crosses the blood-brain barrier and the placenta, and is distributed into breast milk. Propranolol is greater than 90% bound to plasma proteins, primarily alpha-acidic glycoprotein which is elevated in conditions of physiological stress such as inflammation or cancer.

Propranolol is extensively metabolized upon first pass through

the liver by CYP2D6 isoenzymes, with secondary pathways via CYP2C19 and CYP1A2. The drug also binds to and saturates non-specific hepatic binding sites before the drug reaches the systemic circulation. An equipotent, pharmacologically active metabolite, 4-hydroxy-propranolol, is produced with the initiation of oral therapy, but it is eliminated faster than the parent drug because with chronic or IV therapy, this metabolite is produced to a lesser degree.

Excretion of propranolol occurs renally, primarily as metabolites, with only 1-4% of a dose excreted fecally as unchanged drug. The elimination half-life of propranolol ranges from 2-6 hours, with protein binding and chronic administration yielding longer half-lives, possibly due to saturation of liver binding sites and/or systemic clearance. In patients with severe renal dysfunction, fecal elimination may increase to compensate for decreased renal excretory processes. Propranolol is not appreciably removed by hemodialysis. Caution is recommended administering propranolol in patients with altered renal or hepatic function as well as in elderly population because of altered pharmacokinetics, specifically extended half-life/decreased elimination.

4.1.7 Drug Interactions: (www.clinicalpharmacology-ip.com)

Adenosine
Anti-arrhythmic drugs (flecainide, propafenone, moricizine, encainide)
Amiodarone
Bretyllium
Calcium-blocking blood pressure drugs such as diltiazem, nifedipine, and verapamil
Certain high blood pressure medications such as reserpine
Cardiac glycosides
Epinephrine
Insulin
Levodopa
Lidocaine
Monoamine oxidase inhibitors
Oral diabetes drugs such as glyburide
Prazosin
Quinidine
Rifampin
Theophylline

4.1.8 Contraindications and Side Effects:

The adverse effects of propranolol are generally mild and temporary. These side effects usually occur at the onset of therapy and diminish over time. Propranolol is contraindicated in patients with sinus bradycardia, cardiogenic

shock, bronchial asthma, or allergic to propranolol. Use with care in patients with congestive heart failure.

Side Effects: Sinus bradycardia, hypotension, AV block, congestive heart failure in patients with preexisting left ventricular dysfunction, depression, confusion, hallucinations; or Mask signs of hypoglycemia, Agranulocytosis, decreased sex drive, impotence, or difficulty having an orgasm; nausea, vomiting, diarrhea, constipation, stomach cramps; sleep problems (insomnia); or tired feeling.

Please refer to Appendix O & P - Common Side Effects of Beta Blockers.

4.1.9 Supplier:

Propranolol will be provided free of charge to the patients and distributed by the Mays [name] Anderson Cancer Center, and the LBJ Pharmacy. Patients will receive monthly supplies.

4.1.10 Pill Calendar Diary (Appendix M, N):

A pill calendar diary will be submitted at each visit along with the pill bottle for verification. Calendars, empty bottles and any unused medication will be collected at each appointment before the next refill is given to the patient.

4.1.11 Relaxation Practice Log (Appendix Q, R)

The relaxation practice log is to help keep track of relaxation practice. A relaxation practice log will be submitted at each clinic visit.

5.0 PROPOSED TREATMENT/STUDY PLAN

5.1 Dosing of Propranolol

A pill diary will be provided that is a monthly calendar on which patients will record the study medication they take each day. Every dose will be documented and if doses are missed, the patient will be asked to note why they missed a dose. Calendars, empty bottles and any unused medication will be collected at each appointment before the next refill is given to the patient.

Propranolol will be provided to the participant free of charge.

A starting dose of propranolol 20 mg is taken by mouth twice a day (40 mg/day). If the patient tolerates the initial dose (no hypotension or bradycardia) the dose will be increased to 40 mg by mouth twice a day at the start of the second month of therapy. This will ideally be titrated up to 40 mg twice a day in order to maintain a heart rate between 50 to 80 bpm without symptoms or hypotension (systolic BP <110 or diastolic BP <50). For patients > 65 years old the dose will stay at 20 mg by mouth twice a day. Dose reduction to 10 mg administered by

mouth twice a day will be allowed for titration for optimization of BP and pulse. All dose adjustments will be made in the clinic.

To insure compliance, patients will fill out pill calendar diaries that will be collected on a monthly basis.

If removed from study, all patients will be weaned off the medication over the following 2 weeks. The dose will be reduced by 50% for 7 days then will be reduced to 25% of the dose for 7 days then discontinue completely. For patients that experience adverse effects during weaning the period of time can be increased as deemed appropriate.

5.2 Relaxation Intervention

Three 20-minute audio relaxation/guided imagery (R/GI) exercises (MP3) will be provided to each patient (in English or Spanish). Patients will be instructed to listen to the MP3 two times a week and make recordings in a standard diary regarding whether they were able to complete the session and whether they had any difficulties in doing so (difficulties recorded in the diary should include lack of time, unexpected interruption, noise, the presence of children, and other distractions) [99]. To ensure compliance, patients will complete relaxation exercise activity logs as well as pill calendar diaries. These will be collected monthly. (Pill diary)

5.3 Methodology

After a patient is deemed eligible for the study, she will be asked to provide consent to participate. If consent is given, at this time the patient will be given a demographic questionnaire (age, race, marital status, and smoking history) and the Functional Assessment of Chronic Illness Therapy-Cervix (FACT-Cx), Brief Pain Inventory (BPI), MD Anderson Symptom Inventory (MDASI) and Hospital Anxiety and Depression Scale (HADS). Additionally, blood will be drawn from the patient in the clinic prior to the start of the intervention for measurement of baseline IL-6, IL-8, IL-10, circulating HPV DNA, and VEGF levels.

Upon enrollment, all patients will be instructed to listen to MP3-relaxation/guided imagery audio intervention. Patients on protocol will be referred for supportive/palliative care consultation at MDACC or LBJ. At the end of four months, patients will have the option of continuing treatment until intolerability of the treatment, disease progression or death. *Propranolol will be provided to the participants free of charge. Propranolol will be administered at 20 mg twice a day (40 mg/day). This dose will ideally be titrated up to 40 mg twice a day to maintain a heart rate of 50-80 beats per minute without causing hypotension (systolic blood pressure [BP] < 110 mmHg or diastolic BP < 50 mmHg). For patients more than 65 years old, the starting dose will be 20 mg given by mouth twice a day. Dose reduction to 10 mg administered by mouth twice a day will be allowed for titration for optimization of BP and pulse. All dose adjustments will*

be made in the clinic. Blood draws and completed surveys of biobehavioral measures (FACT-Cx, MDASI, HADS, BPI and smoking history) will be collected at baseline and again after the completion of every two cycles (1 month = one cycle) until the 4-month time point. The HADS will be scored and evaluated within 24 hours of completion. The Hospital Anxiety and Depression Scale (HADS) is a 14 item self-administered scale to detect states of depression and anxiety. Respondents answer questions using a scale of 0 (not at all) to 3 (very often). A HADS score of 15 or higher defines clinical depression or anxiety, and those patients will be assessed by their physician, and, if appropriate, referred to psychiatry. Scoring will be done by the research personnel.

Feasibility is determined by completion of three time points (TP0, 2, 4 mos). Patients who wish to continue on the regimen may do so until voluntary discontinuation, intolerability, disease progression, or death. The patient will be followed until death with assessment of medical notes in clinic station. Reason for study termination will be recorded.

CT of chest, abdomen, and pelvis will be obtained at baseline within 6 weeks prior to starting treatment and then per MD discretion or worsening of symptoms.

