**Effect of a Beta Adrenergic Blockade combined with Relaxation/Guided Imagery
Audio Intervention on symptom distress in Women with Advanced, Recurrent
Incurable Cervical Cancer-Feasibility study**

Principal Investigator:

[name].
Division of Gynecologic Oncology
and Reproductive Medicine
MD Anderson Cancer Center
[name]
[contact]
Email: [contact]

Co-Investigators: MD Anderson Cancer Center

[name]
[name]
[name]
[name]
[name]
[name]
[name] MS

Statistician:

The Harris Health System

[name], DO

SCHEMA

Blood drawn prior to administration of Propranolol after consented for study

Fill out questionnaires

Instruct on use of R/GI MP3 use and diary

Propranolol 20mg po bid initiated

Patient instructed to listen to MP3 2x a week and record in diary

Increase propranolol to 40 mg po bid if the patient is tolerating at one month time point.

Continue oral Propranolol until removal from study

Blood drawn and completion of questionnaires after the completion of every two cycles (2 mos and 4 mos)

TABLE OF CONTENTS

1.0	OBJECTIVES
2.0	BACKGROUND AND RATIONALE
3.0	PATIENT ELIGIBILITY
4.0	STUDY MODALITIES
5.0	PROPOSED TREATMENT/STUDY PLAN
6.0	SAFETY PLAN AND CRITERIA FOR REMOVAL FROM STUDY
7.0	TREATMENT MODIFICATIONS
8.0	STUDY PARAMETERS AND SERIAL OBSERVATIONS
9.0	EVALUATION CRITERIA
10.0	DURATION OF STUDY
11.0	STUDY MONITORING AND REPORTING PROCEDURES
12.0	STATISTICAL CONSIDERATIONS
13.0	DATA MANAGEMENT
14.0	TRANSLATIONAL RESEARCH
15.0	PROTOCOL COMPLIANCE
16.0	REFERENCES

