7.0 TREATMENT MODIFICATIONS

Propranolol can be dose reduced if the patient's heart rate is less than 60 or systolic BP is less than 110 or diastolic less than 50 and showing symptoms at two different timepoints 24 hours apart. Also if the patient has side effects from the beta-blocker a dose reduction can be performed as outlined in Table E. All dose reductions will be made in the clinic. The maximum dose for propranolol should be 40mg po twice a day. For patients > 65 years old the maximum dose will be 20 mg by mouth twice a day. All dose adjustments will be made in the clinic.

Table E Modifications for Propranolol dosing

	Regimen -1 Level	Regimen -2 Level
Starting Dose 20 mg twice daily	10 mg po bid (50%)	Discontinue
Maximum Dose 40 mg twice daily	30 mg po bid (25%)	20 mg po bid (50%)

7.1 Hypotension.

Patients receiving propranolol should be monitored before each dose with measurement of blood pressure (see Section 5.0 Treatment Plan). If the SBP is less than 110 or the DBP is less than 50 and showing symptoms at two different timepoints 24 hours apart, the patient should be dose modified to regimen level -1 (see Table E). If after this dose modification there is still hypotension, then dose modify to regimen level -2 (see Table E). If patient still encounters hypotension, then discontinue the propranolol.

7.2 Bradycardia.

Patients receiving propranolol should be monitored with a measurement of heart rate. If the heart rate is less than 50 or 50-60 and showing symptoms at two different timepoints 24 hours apart, the patient should be dose modified to regimen level -1 (see Table E). If after this dose modification there is still bradycardia, then dose modify to regimen level -2 (see Table E). If patient still encounters bradycardia, discontinue propranolol.

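### The propranolol rule for patients over 65 is inconsistent: three sections hold the dose at 20 mg twice daily, while Section 5.3 and the Schema leave 40 mg twice daily open

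*Combined protocol and SAP*

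**What the plan says.** Three places restrict the dose over age 65:

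- Section 4.1.4 (Administration): "For patients >65 years old the dose will stay at 20 mg by mouth twice a day".
- Section 5.1 (Dosing of Propranolol): "For patients > 65 years old the dose will stay at 20 mg by mouth twice a day".
- Section 7.0 (Treatment Modifications) gives a general ceiling, "The maximum dose for propranolol should be 40mg po twice a day", and then a lower one by age: "For patients > 65 years old the maximum dose will be 20 mg by mouth twice a day".

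Two places do not:

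- Section 5.3 (Methodology) starts every patient on 20 mg twice daily and continues: "This dose will ideally be titrated up to 40 mg twice a day to maintain a heart rate of 50-80 beats per minute", provided hypotension is not caused. The age sentence that follows is: "For patients more than 65 years old, the starting dose will be 20 mg given by mouth twice a day".
- The Schema has one escalation line, with no reference to age: "Increase propranolol to 40 mg po bid if the patient is tolerating at one month time point".

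Three other parts of the protocol bear on the point. The only age limit in Section 3.2 excludes patients under 18. Section 4.1.6 advises caution in older patients because they eliminate the drug more slowly. Section 12.0 makes safety part of the feasibility definition, through a posterior-probability criterion on related grade 3-4 toxicities.

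**The concern.** Sections 5.1 and 5.3 are close to parallel, but the age sentence changes meaning between them. In 5.1 it fixes where the dose remains; in 5.3 it fixes where the dose begins. Because every patient begins at 20 mg twice daily, the 5.3 sentence separates older patients from no one. It also comes directly after the titration sentence, so it can be read as the first step of the same escalation. Someone reading only 5.3, or only the Schema, sees no sign that a lower ceiling exists elsewhere.

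Two things are at stake. The first is the dose given to an older patient, in a group for whom the protocol itself urges caution. The second is interpretation. A related grade 3-4 event in a patient over 65 enters the Section 12.0 toxicity criterion whichever section was followed. If the protocol allows two readings, it is unclear which regimen that event informs.

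**Working it through.** **Inputs**

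- Starting dose for all patients: 20 mg twice daily, which Section 5.3 gives as 40 mg/day.
- Highest dose open under the Schema and Section 5.3: 40 mg twice daily.
- Maximum over age 65 in Section 7.0: 20 mg twice daily.

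**Reproducing the plan's own figure**

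Daily dose = dose per administration × administrations per day. For the starting dose, 20 × 2 = 40 mg/day, which matches Section 5.3.

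**Size of the discrepancy**

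- Reachable under the Schema or Section 5.3 read alone: 40 × 2 = 80 mg/day.
- Ceiling over age 65 in Section 7.0: 20 × 2 = 40 mg/day.
- Ratio: 80 / 40 = 2.

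**The five places side by side, for a patient over 65 who tolerates the first month**

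| Place | What it says about age over 65 | Highest daily dose on that text alone |
|---|---|---|
| Schema | Nothing | 80 mg |
| 4.1.4 | Dose remains at 20 mg twice daily | 40 mg |
| 5.1 | Dose remains at 20 mg twice daily | 40 mg |
| 5.3 | Starts at 20 mg twice daily | 80 mg |
| 7.0 | Maximum is 20 mg twice daily | 40 mg |

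The increase is conditional in both permissive places. The Schema requires tolerance at one month; Section 5.3 depends on heart rate and blood pressure. So 80 mg/day is the most those texts allow, not what every older patient would receive.

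**Can it occur in this trial?** Section 3.2 sets a lower age limit only, and four numbered sections carry a sentence about patients over 65, so such patients are expected. The documents give no age distribution for the trial population, and the number affected among the 20 recruited cannot be estimated. It could be zero.

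**Link to the analysis.** Section 12.0 requires Pr(π_t ≤ 0.2 | data) > 90%, where π_t covers grade 3-4 toxicities judged possibly, probably or definitely related. A qualifying event in a patient over 65 would count. Milder or unrelated events would not.

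**The case against.** The strongest reply is that the limit is explicit in three places, including the section devoted to dosing and the one on dose modification, and that a specific age rule normally qualifies a general escalation line. Section 5.1 itself has an unqualified titration sentence followed by an age sentence, and it still carries a limit. On this view 5.3 contains a drafting slip in one phrase, and the Schema is an outline that also omits the blood-pressure and heart-rate thresholds and the dose reductions.

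Much of this stands. The unqualified titration sentence in 5.3 is not the defect on its own, and a slip is more plausible than a deliberate second rule. But the slip is in operative dosing text, and it removes the limit from the only sentence in 5.3 that deals with age.

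Some stronger readings are tempting and are not supported:

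- A reader might infer that a site following the Schema or 5.3 would give twice the maximum, or that the protocol instructs this. Neither text directs 40 mg twice daily for a patient over 65. They permit it by silence, and a site that also reads 4.1.4, 5.1 or 7.0 would see the limit. The supportable word is could.
- A reader might infer that staff dose from the Schema, or that the two dispensing pharmacies named in 4.1.9 will diverge. The documents say neither.
- A reader might infer that any hypotension or bradycardia counts against the safety criterion. Only related grade 3-4 events do.
- A reader might size the problem as one event in 15 evaluable patients, 1/15 = 6.7 percentage points. That is the weight of any single event in any patient and does not measure this defect. Section 12.0 also does not fix the denominator; with all 20 recruited patients it would be 1/20 = 5 points.
- The upper age of 83 in Section 2.10 belongs to a laboratory series sampled at diagnosis, with a median age of 45.3. It says nothing about how many patients over 65 will enrol here.

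**Conclusion.** The inconsistency is real and should be corrected. For a patient over 65, the highest daily dose allowed is 40 mg on the text of 4.1.4, 5.1 and 7.0, and 80 mg on the text of 5.3 or the Schema read alone, a factor of 2. This rests only on the wording of the five places and on simple multiplication.

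Its practical reach is not known. It needs a patient over 65 to enrol and tolerate the first month, and a prescriber to rely on one of the two permissive places without the other three. The documents do not allow a probability for any of these. The effect on the toxicity criterion is likewise a possibility and has not been quantified. This is a correction the plan should make on grounds of patient safety and clarity. It is not evidence that older patients will be given the higher dose, and it implies no view on which rule is clinically right.

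**What to change.** Reconcile the Schema and Sections 4.1.4, 5.1, 5.3 and 7.0 so that all five state one rule for patients over 65 in the same words. The clinical team decides which rule.

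The cost is a short text amendment. If the rule in 4.1.4, 5.1 and 7.0 is kept, the two other places change; if the reading left open by 5.3 and the Schema is the intended one, those three sections change. Sample size, endpoints and analysis are unaffected. If patients over 65 have already been treated, their records should show which dose they received, so that any toxicity can be attributed to a known regimen.
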